subscore of the Constant-Murley score remained significantly improved. They were unable to associate the grade of OA to pain relief following IACSI.

This study differs dramatically from clinical practice, where IACSI is normally administered as a single injection. Repeat injections are often delayed, with some surgeons recommending a three month break between injections. Presently, there is an evidence gap with respect to evidence of the effectiveness of single-injection IACSI on clinical and patient-reported outcomes in patients with glenohumeral OA.

5. Specific Aims

To address this deficit in the literature, there are two specific aims:

1. Assess the effectiveness of IACSI in patients with primary osteoarthritis in the shoulder. This will be determined through three patient-reported outcomes measures:
 - ASES (American Shoulder & Elbow Surgeon) score improvement > 20.9 points⁸
 - VAS (Visual Analog Scale) pain score improvement > 1.4 points
 - SST (Simple Shoulder Test) score improvement > 2.4 points
2. Assess clinical and radiographic predictors of success (outlined below) in patients who elect to receive IACSI as treatment for primary osteoarthritis in the shoulder.
 - Clinical
 - Duration of Symptoms
 - Location of pain (Anatomic Diagram, Figure 1)
 - Pain diagrams will be analyzed using a computer overlay protocol and analyzed in a binary matter according to region. Image software (NIH, Bethesda, MD) will be used. Proportions of the patients responding to injection in each anatomic region and groups of regions will be calculated. 95% confidence intervals will be determined.¹
 - History of prior injection
 - Range of motion (Forward elevation in the scapular plane, ER at 0° abduction, IR at 0° abduction)
 - Standardized pain and function scores (VAS pain, SST, ASES)
 - Prior analgesia (OTC, Narcotic)
 - Initial response to anesthetic component (VAS 5-10 min post-injection)
 - Radiographic
 - Joint space narrowing (measured)
 - Subluxation
 - Walch classification
 - Subchondral cysts
 - Samilson & Prieto Radiological Classification
 - Mild Arthrosis: inferior humeral and/or glenoid exostosis < 3mm in height

- Moderate Arthrosis: inferior humeral and/or glenoid exostosis measuring 3mm to 7mm slight gleno-humeral irregularity
- Severe Arthrosis: inferior humeral and/or glenoid exostosis measuring > 7mm gleno-humeral joint narrowing and sclerosis

6. Research Plan

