Subjects: Five hundred patients, both male and female, age 18-100 years, with a diagnosis of symptomatic primary osteoarthritis of the shoulder will be recruited from the patient population seeking treatment at the Orthopaedics Sports Medicine Institute. Subjects enrolled into the study will be those who have failed previous treatment including over-the-counter analgesics and activity modification, and have elected to receive a medically-indicated, ultrasound-guided IACSI in the shoulder. Two or three plain film views of the shoulder (including a Grashey and axillary lateral) obtained in accordance with standard of care prior to enrollment in the study will be reviewed. Once written informed consent has been obtained, subjects will complete the pre-procedural pain chart (Figure 1), ASES, VAS pain (at rest, with activity, at night), and SST scores. Upon completion of all outcomes measures, the ultrasound-guided IACSI (5cc of 1% lidocaine, 2cc of depomedrol (40mg/mL)) will be administered. Subjects will be asked to repeat the VAS pain score (at rest) 5-10 minutes following administration of the injection to assess the response to the anesthetic component of the injection. Upon conclusion of the visit, no clinical follow-up appointment will be scheduled, and subjects will be instructed to follow-up with their physician as needed; this is in accordance with standard of care for this patient population.

MRN: _____
 Date: _____
 Diagnosis: _____
 Injection: _____
 Pain: Pre: _____ post: _____
 Global: Yes No

Please shade in the areas where you are feeling pain now.
 Please mark with a dark circle (●) the areas where the pain is the worst.

(Figure 1: Pre-procedural pain chart, anatomic diagram)

Subjects will be contacted via email through the REDCap survey function or a phone call at two weeks, one month, two months, three months, and six months following the injection to complete the ASES, VAS pain (at rest, with activity, at night), and SST scores. If an email survey is not completed in REDCap, a reminder email will be sent every two days, up to two

times. If, after the final email reminder, the REDCap survey is still incomplete, a member of the study staff will call the subject and complete the survey via telephone call.

Exclusion Criteria: Patients will be excluded from the study for any of the following reasons:

- Post traumatic osteoarthritis
- Inflammatory osteoarthritis
- Imaging confirmed rotator cuff tear
- Prior ipsilateral shoulder surgery

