- Memory loss or inability to complete study measures
- History of allergy to injection medications
- Diabetic patients with patient-reported fasting blood glucose >200
- Prior injection in the ipsilateral shoulder within three months

Data Collection: The following data points and information will be collected for later analysis:

- Patient name
- MRN
- Gender
- Date of birth
- E-mail address
- Telephone number
- Location of pain (pre-procedural pain chart)
- Duration of symptoms
- History of prior IACSI in ipsilateral shoulder
- Prior analgesia
- Shoulder Range of Motion (Forward elevation, External rotation, Internal rotation)
- Radiographic findings
- Date of IACSI
- Date of each follow-up survey
- Results of each standardized pain and function survey

Confidentiality: Once all enrolled subject data is collected, subject PHI will be removed and the data will be maintained by using assigned research identification numbers that uniquely identify each individual. Date of birth will be converted to age, and dates will also be converted to time frames. Coded data will be stored on a secure online database such as REDCap and an Excel spreadsheet on a password protected computer within the Department of Orthopaedics and Rehabilitation. Data will be converted to a SPSS file for analysis which will also be stored on a secure department server. Data will be used only in aggregate and no identifying characteristics of individuals will be published or presented. Only the study team members will have access to these files. After the study is completed, local data will be stored with other completed research studies in a secured storage room until the appropriate time when the research files may be purged according to university policy.

Data Analysis:

Each patient-reported outcome measure will be assessed at each time point pre- and post-injection and grouped according to the grade of shoulder osteoarthritis. Groups will be compared using a one-way ANOVA analysis. Groups with a response to injection (VAS score improvements greater than the minimal clinically important difference) will be compared to those without a significant response. Single multi-level regression analysis will be performed to assess for clinical and radiographic risk factors outlined in Aim Two that may predict corticosteroid injection failure.

7. Possible Discomforts and Risks

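### Name Welch's ANOVA for the comparison of osteoarthritis grades: the usual one-way ANOVA loses its 5% error rate if group sizes and SDs both differ between grades

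*Combined protocol and SAP*

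**What the plan says.** Section 6 (Research Plan), Data Analysis, sets out the comparison in two sentences: "Each patient-reported outcome measure will be assessed at each time point pre- and post-injection and grouped according to the grade of shoulder osteoarthritis", and then "Groups will be compared using a one-way ANOVA analysis". It does not say whether the classical or the Welch form is meant. It gives no check of variances, no fallback test and no method for pairwise comparisons.

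The paragraph does not name the grading scale. Section 5 (Specific Aims) lists the "Samilson & Prieto Radiological Classification" with mild, moderate and severe classes, so three groups is the natural reading.

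On group sizes, the Subjects paragraph of section 6 gives a total of 500 patients, "recruited from the patient population seeking treatment at the Orthopaedics Sports Medicine Institute". It sets no target or quota per grade. Scores are collected before injection and again "at two weeks, one month, two months, three months, and six months following the injection". Neither an expected grade distribution nor an SD for any score appears anywhere.

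**The concern.** The classical one-way F test estimates a single SD from all grades together. That estimate is dominated by the largest group. If a small grade group is more variable than the rest, the pooled SD understates the uncertainty of its mean, and the test declares grade differences too often. If the small group is less variable, the test is too cautious.

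Two conditions must hold together: unequal sizes and unequal SDs. The first is likely here, since equal thirds from an unselected clinic population would be a coincidence. The second is plausible but not documented. The plan divides patients into responders and non-responders, and Aim 2 treats radiographic grade as a possible predictor of response. Grades with different shares of responders would generally have different spread after injection.

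At stake is whether a reported p-value for a grade difference means what it says. A total of 500 does not protect against this, because the distortion depends on the ratios of sizes and SDs.

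**Working it through.** There is no figure of the plan to reproduce: the 500 comes with no alpha, power, SD or grade split.

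**Inputs.** From the documents: one-way ANOVA by grade; 500 patients; no grade quota. Assumed: three grades, a two-sided 5% level, and all group sizes, SDs and responder shares below.

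**Why both conditions are needed.** With k grades, sizes nᵢ, total N and true SDs σᵢ, when the true grade means are equal:

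- expected between-grade mean square = Σσᵢ²(1 − nᵢ/N)/(k − 1)
- expected pooled mean square = Σ(nᵢ − 1)σᵢ²/(N − k)

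A valid test needs the two to match. For sizes 50/150/300:

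- Equal SDs of 1: (0.9 + 0.7 + 0.4)/2 = 1.00 against 1.00. They match.
- SDs 1.5/1.25/1: (2.25×0.9 + 1.5625×0.7 + 1×0.4)/2 = 1.76 against (49×2.25 + 149×1.5625 + 299×1)/497 = 1.29. The ratio is 1.36, so the test rejects too often.
- SDs 1/1.25/1.5: (1×0.9 + 1.5625×0.7 + 2.25×0.4)/2 = 1.45 against (49×1 + 149×1.5625 + 299×2.25)/497 = 1.92. The ratio is 0.75, so it rejects too rarely.

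**Simulated error rates.** Normal scores, equal true means, nominal 5%, 10,000 runs per setting:

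| Sizes (N = 500) | SDs, same order | Classical F | Welch |
|---|---|---|---|
| 50/150/300 | 2/2/2 | 4.9% | 4.9% |
| 50/150/300 | 2.5/2.25/2 (ratio 1.25) | 8.3% | 5.2% |
| 50/150/300 | 2/2.25/2.5 | 2.9% | 5.1% |
| 50/150/300 | 3/2.5/2 (ratio 1.5) | 11.5% | 5.1% |
| 50/150/300 | 2/2.5/3 | 2.0% | 5.0% |
| 100/150/250 | 3/2.5/2 | 8.3% | 5.1% |
| 100/150/250 | 2/2.5/3 | 3.2% | 5.0% |
| 167/167/166 | 2/2.5/3 | 5.6% | 5.4% |

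Repeat runs of the 11.5% setting with 20,000 data sets gave about 11%. With 350 analysed (an assumed 30% loss) at the 10/30/60 split and SD ratio 1.5, the classical test gave 2.4% and 11.4%. On a rounded 0–10 scale with 500 patients it gave 2.4% and 10.5%.

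**Responder mix.** A grade with responder share p, a gap d between responder and non-responder means, and a common component variance s² has variance p(1 − p)d² + s². Take d = 4 and shares of 50% and 15%. With s = 1.5 the SD ratio is √[(4 + 2.25)/(2.04 + 2.25)] = 1.21; with s = 2 it is √[(4 + 4)/(2.04 + 4)] = 1.15.

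To obtain an error rate, the grade means must be equal. For post-injection scores this can happen if differences in starting level offset differences in response. Simulating mixtures of this kind with equal grade means gives about 3.2% to 7.2% for the classical test and about 5% for Welch.

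**Cost of Welch when SDs are equal.** With SD 2.5 and means 0/0.4/0.8, power is 74.8% (classical) against 74.5% (Welch) in balanced groups, and 56.5% against 55.6% at 50/150/300. The second is a loss of 0.9 points, the largest seen.

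**The case against.** The strongest reply is that nothing in the documents shows unequal SDs. The plan contains no wrong figure here, and choosing Welch could be left to the analyst. The first two parts are true, and they limit the point to a precaution. The third is weaker: a choice between tests made after seeing the data adds discretion that one phrase would remove.

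A sharper reply concerns the responder mechanism. If one grade has 50% responders and another 15%, with a 4-point gap, mean change differs by 0.35 × 4 = 1.4 points. On change scores the null hypothesis is then false, so that mechanism cannot produce a false grade effect. In simulations with these uncentred mixtures (30% responders in the middle grade) the two tests had similar power: 97.3% classical against 96.0% Welch at 50/150/300, and 98.1% against 98.4% with the mix reversed. This stands for change scores. It does not dispose of the point, because the plan compares scores at each time point, where post-injection means can be equal while responder mixes differ.

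A reader might also infer several stronger things that the documents do not support:

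- That uncontrolled group sizes are enough. They are not: with equal SDs the classical test holds about 5% at every split.
- That confidence intervals from this analysis would be too narrow. No ANOVA-based interval is planned; the 95% intervals in section 5 are for responder proportions by pain region.
- That responder mixing by itself gives an SD ratio of 1.25. With the shares and gap above, that value also needs different SDs within responders and within non-responders.
- That every grade comparison is affected. Pre-injection scores cannot carry a responder mix.
- That the plan prescribes equal variances. That is the usual reading of the term, not something the text states.

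**Conclusion.** The point holds as a minor, conditional one. The plan names a test whose usual form relies on equal SDs, in a design that leaves group sizes to the case mix. If SDs also differ between grades, the actual error rate of a nominal 5% test could be about 3% to 7% under modest differences in responder mix with equal means. It could be about 2% to 11.5% at an SD ratio of 1.25 to 1.5 with sizes 50/150/300. The direction depends on whether the small or the large grade group is the more variable.

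These figures rest on assumed sizes, SDs and responder shares, and on reading grade as three classes. They show what the test is exposed to, not what will happen in this study. If SDs turn out equal, or groups turn out balanced with SD ratios in this range, the classical test would be at or close to 5%.

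**What to change.** In section 6, Data Analysis, replace one-way ANOVA by Welch's ANOVA, and add that any pairwise comparisons between grades will use the Games-Howell procedure. No SD or grade distribution needs to be known in advance, and neither recruitment nor data collection changes. The cost is one phrase in the plan and, if variances are equal, a power loss of under about 1 point.

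### The grade comparison uses only an omnibus one-way ANOVA; a prespecified linear grade term, adjusted for baseline, should be reported alongside it

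*Combined protocol and SAP*

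**What the plan says.** In Research Plan, Data Analysis, the first comparison takes the scores as follows: "Each patient-reported outcome measure will be assessed at each time point pre- and post-injection", and "grouped according to the grade of shoulder osteoarthritis". The test is then named: "Groups will be compared using a one-way ANOVA analysis". No linear contrast, trend test or ordinal coding of grade appears anywhere, and baseline is not named as a covariate.

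Data Analysis does not say which grading is meant. The only scale with defined mild, moderate and severe levels is the Samilson & Prieto classification under Specific Aims, aim 2:

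- "Mild Arthrosis: inferior humeral and/or glenoid exostosis < 3mm in height"
- "Moderate Arthrosis: inferior humeral and/or glenoid exostosis measuring 3mm to 7mm"
- "Severe Arthrosis: inferior humeral and/or glenoid exostosis measuring > 7mm"

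The moderate level also mentions slight joint irregularity, and the severe level mentions narrowing and sclerosis. The levels are therefore ordered, but not purely by millimetres.

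A separate model follows: "Single multi-level regression analysis will be performed to assess for clinical and radiographic risk factors". Its outcome is injection failure, and the coding of grade in it is not stated.

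**The concern.** An omnibus test on three groups spends two degrees of freedom on any difference among the means. A graded relation between radiographic severity and outcome needs only one. A significant F also gives no direction and no per-grade estimate, whereas a slope gives both, with a confidence interval.

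Sensitivity matters here because Background and Significance reports that the one earlier steroid-injection study could not link grade to pain relief.

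The second gap is baseline. An ANOVA of scores at a follow-up time compares grades on where patients are then. Grades that differed before injection can differ afterwards for that reason alone, and the prognostic information in the baseline score goes unused.

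**Working it through.** **Inputs.** N is 500 (Research Plan, Subjects). There are three grades (Specific Aims). The documents give no alpha, power, effect size, SD or grade distribution, and no power calculation, so there is no figure of the plan's own to reproduce. Assumed: two-sided alpha 0.05 and 80% power for the ANOVA. Grade mixes are varied.

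**Step 1: evenly graded effect (0/1/2).** All of the between-grade signal lies in the linear term, so both tests have the same noncentrality λ.

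- 2 df: λ such that P(noncentral χ² on 2 df > 5.991) = 0.80 is 9.635.
- 1 df: λ = (1.960 + 0.842)² = 7.849.
- Ratio: 7.849 / 9.635 = 0.815, so 18.5% fewer patients; 0.815 × 500 ≈ 407.
- Trend power where the ANOVA has 80%: Φ(√9.635 − 1.960) = Φ(1.144) = 87.4%.

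Exact noncentral F (2 and 497 df against 1 and 497 df) gives the same 407 and 87.4%. For an exactly linear effect the ratio does not depend on SD, dropout or grade mix. At alpha 0.05 the saving is 19.9% at 70% power, 17.0% at 90% and 15.9% at 95%. At 80% power it is 19.8% for alpha 0.10 and 15.9% for alpha 0.01.

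**Step 2: other shapes.** With grade shares w, scores x = 0, 1, 2 and means μ, the trend keeps this share of the signal:

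[Σw(x−x̄)(μ−μ̄)]² / [Σw(x−x̄)² · Σw(μ−μ̄)²]

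- Step at severe (0/0/1), equal groups: (1/3)² / (2/3 × 2/9) = 0.75.
- The same step at 40/50/10: x̄ = 0.7, μ̄ = 0.1; 0.13² / (0.41 × 0.09) = 0.458.

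With the ANOVA held at 80% power on 500 patients (exact F):

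| Pattern | Mild/moderate/severe shares | Trend power | N for 80% |
|---|---|---|---|
| 0/1/2 | any | 87% | 407 |
| 0/0.5/2 | equal | 85% | 441 |
| 0/0.5/2 | 60/30/10 | 83% | 459 |
| 0/0.5/2 | 40/50/10 | 82% | 479 |
| 0/1.5/2 | 60/30/10 | 85% | 433 |
| 0/0/1 | equal | 77% | 542 |
| 0/0/1 | 50/30/20 | 73% | 586 |
| 0/0/1 | 60/30/10 | 64% | 731 |
| 0/0/1 | 40/50/10 | 56% | 886 |
| 0/1/0 | equal | 5% | none |

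The uneven monotone rows save from 1 − 479/500 = 4% to 1 − 433/500 = 13%. The step rows lose from 80 − 77 = 3 points to 80 − 56 = 24 points.

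**Step 3: effect size at N=500.** For equal groups and d SD per grade, λ = 500 × d² × 2/3.

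| d | λ | ANOVA | Trend |
|---|---|---|---|
| 0.125 | 5.21 | 51.9% | 62.5% |
| 0.15 | 7.50 | 68.5% | 78.0% |
| 0.20 | 13.33 | 91.3% | 95.4% |
| 0.25 | 20.83 | 98.8% | 99.5% |

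The gap peaks near 10 points for small effects and is under 1 point at 0.25 SD per grade.

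**Step 4: slope or contrast.** For a linear effect at 60/30/10, a −1/0/1 contrast of group means carries 2² / (1/0.6 + 1/0.1) = 0.343 per patient. The slope carries Σw(x−x̄)² = 0.7 − 0.5² = 0.45. The contrast keeps 0.343 / 0.45 = 76% of the information, so the trend should be fitted as a slope.

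**Baseline.** No correlation between baseline and follow-up is given, so the gain from adjustment is not quantified.

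**The case against.** The strongest reply is that nothing here is an error. An omnibus ANOVA across three grades is valid, keeps its Type I error and assumes no shape. That stands: the point concerns efficiency and interpretation.

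Three stronger readings are tempting, and the documents do not support them.

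- **That the trend test should replace the ANOVA at almost no cost.** The 3-point loss under a step holds only for equal groups. The documents give no grade distribution, and the mixes above reach 24 points, more than the 7-point gain for an evenly graded effect. The severe level adds narrowing and sclerosis to its size criterion, so a step there is plausible.
- **That the plan expects benefit to fall as grade rises and forfeits nearly a fifth of its patients.** No directional hypothesis for grade is stated. The 18.5% applies to evenly spaced effects at an assumed alpha and power, and 500 is not justified by this comparison.
- **That the plan ignores the ordering everywhere.** The regression for injection failure might enter grade as an ordered term; its coding is not stated. The loss of ordering is established only for the score comparison, which that regression does not replace because its outcome is different.

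It can also be said that baseline adjustment is a separate matter. It is, but it belongs in the same sentence of the same analysis and uses scores already collected.

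**Conclusion.** The point holds as a modest improvement to a valid analysis. The grade comparison as written does not use the ordering of the grades and does not adjust for baseline. For an evenly graded effect, a linear term raises 80% power to 87%, worth about 18.5% of the patients. For the uneven monotone patterns tried it is worth about 4–13%, and with large effects at N=500 the power gain is negligible. If the pattern is a step or non-monotone, the trend read alone is the weaker test in most of the mixes tried, sometimes by a wide margin. That supports adding the trend but not substituting it.

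The conclusion rests on reading the grade in Data Analysis as the Samilson & Prieto scale, on an assumed two-sided alpha of 0.05, and on assumed effect shapes and grade mixes.

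**What to change.** In Data Analysis:

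1. Name the grading scale used for the comparison.
2. Prespecify a 1-df linear term for grade, fitted as a regression slope on grade scored 1-2-3. The outcome is the follow-up score, or the change, with the baseline score of the same measure as covariate. Report the slope with its confidence interval.
3. Report the 2-df overall test of grade beside it, and state in advance what role each test plays, so that neither is chosen after the results are seen.

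This takes a sentence or two and needs no new data, visits or patients. The costs are one extra test for each outcome and time point analysed, and the risk of missing a step or non-monotone pattern if the trend is read alone. Keeping the 2-df test guards against the latter.

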Protocol

1. Project Title:

Predicting Response to Intra-Articular Corticosteroid Injection in Patients with Osteoarthritis of the Glenohumeral Joint

2. Investigators:

PI: [name].
Co-I: [name].
[name].
M. [name].
[name].
[name].
[name].
[name].
[name].
[name].
[name].

3. Abstract

In 2009, the AAOS made formal recommendations for osteoarthritis of the glenohumeral joint, but was unable to formally recommend physical therapy, pharmacotherapy or corticosteroid injection. Despite a lack of clinical evidence, orthopedic surgeons continue to recommend conservative treatments prior to considering surgical intervention for primary osteoarthritis of the glenohumeral joint. Generally, activity modification, over the counter analgesics, and intraarticular corticosteroid injections (IACSI) are offered prior to considering arthroplasty.^{5,6} The scientific literature remains limited regarding IACSI success for glenohumeral arthritis, with practices largely being adopted from the lower extremity literature. There remains only one small study assessing outcomes following IACSI, where success was indicated as significant pain reduction, improvement in the Constant-Murley scale, Shoulder Pain and Disability Index (SPADI) scores and satisfaction with treatment.³ The purpose of this study is to assess the effectiveness of IACSI for glenohumeral arthritis by 1) measuring clinical and radiographic parameters and 2) identifying predictors of IACSI success.

4. Background and Significance

Research regarding IACSI for glenohumeral OA is limited. While many articles have assessed the role of hyaluronic injections for this condition, only one study has assessed the effectiveness of IACSI.^{4,3,7,2} In this study, IACSI was retrospectively compared to intra-articular hyaluronic acid (HA) injections.³ All injections were administered in an unguided fashion. Corticosteroid dose for each injection was 40 mg of Depomedrol. Both groups received three injections one week apart, including the steroid group. Within the IACSI group, pain relief was only found to be significant at one month (6.25 vs 4.4, p=0.04). The clinical significance of this change remains debatable. This improvement was significant for both pain at night, as well as pain with activity. No significant differences remained at three months or six months. SPADI scores showed no significant changes over time. The range of motion

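### Aim 2 response is a VAS drop split at 1.4 points, so baseline pain is part of the outcome, and the split loses information on the predictors other than OA grade

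*Combined protocol and SAP*

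**What the plan says.** The Data Analysis part of section 6 separates "Groups with a response to injection (VAS score improvements greater than the minimal clinically important difference") from patients without a response and compares the two. No baseline adjustment is stated for this comparison. Aim 1 in section 5 gives the threshold: "VAS (Visual Analog Scale) pain score improvement > 1.4 points".

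The plan continues: "Single multi-level regression analysis will be performed to assess for clinical and radiographic risk factors". These are the "clinical and radiographic risk factors outlined in Aim Two that may predict corticosteroid injection failure". No outcome type, link function or definition of the levels is given. Coming straight after the responder definition, failure is most naturally read as a yes/no outcome, but that is an inference.

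The clinical predictors under Aim 2 include "Standardized pain and function scores (VAS pain, SST, ASES"). Section 6 (Subjects) has VAS recorded before the injection and again at "two weeks, one month, two months, three months, and six months following the injection", each time for pain at rest, with activity and at night. The visit and the VAS item that define response are not named.

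One analysis does stay on the score scale: each patient-reported outcome at each time point is compared across OA grades by one-way ANOVA.

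**The concern.** A drop from baseline contains the baseline value. A patient whose pre-injection score is high partly by chance tends to score lower later, whatever the injection did, and so crosses a fixed threshold more easily. In the simple responder comparison, the two groups will differ in baseline pain, and any factor correlated with baseline pain inherits that difference.

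Reducing a pain score to yes or no also discards how far each patient moved, which makes modest effects of the other predictors harder to detect.

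Section 8 gives the study's expected benefit as helping providers predict response. Two outcomes would undermine it: a baseline-pain result taken to mean that worse pain benefits more, and clinical or radiographic factors with small real effects being missed.

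**Working it through.** **Inputs from the documents.** Threshold 1.4 points; 500 patients; five follow-up visits; means 6.25 before and 4.4 at one month in the prior study (Background), a drop of 1.85, used only as an illustration.

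**Assumed, because the documents give no figure.** SD 2.5 at every time; correlation r between baseline and follow-up of 0.4 to 0.8; normal scores; the same true drop for everyone; a yes/no predictor present in 30%; two-sided 5% test. The plan gives no basis for the 500, so there is no figure of its own to reproduce.

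**Step 1: coupling.** With equal SDs, the correlation of baseline with drop is √((1−r)/2): 0.55 at r = 0.4 and 0.32 at r = 0.8. Since 1.85 − 1.4 = 0.45,

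P(response | baseline x) = Φ{[0.45 + (1−r)(x − 6.25)] / [2.5√(1−r²)]}.

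One SD below the mean, at the mean and one SD above (3.75, 6.25, 8.75), this gives 32%, 58% and 80% at r = 0.4, and 49%, 62% and 74% at r = 0.8. It rises with x for any r below 1. A logistic fit to 400,000 simulated patients gives odds ratios per baseline point of 1.545 (r = 0.4) and 1.246 (r = 0.8).

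Mean baseline by group at r = 0.4: the SD of the drop is 2.5√1.2 = 2.739, 0.45/2.739 = 0.164, the response rate is Φ(0.164) = 0.565 and φ(0.164) = 0.394.
- Responders: 6.25 + 2.5 × 0.5477 × 0.3936/0.5653 = 7.20.
- Non-responders: 6.25 − 2.5 × 0.5477 × 0.3936/0.4347 = 5.01.

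At r = 0.8 the simulation gives 6.75 and 5.46.

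**Step 2: loss from the split.** Both models are adjusted for baseline VAS. For a 0.5-point effect at r = 0.4:
- Continuous, one visit: residual SD 2.5√(1−0.16) = 2.29; SE 2.29/√(500×0.3×0.7) = 0.2236; 0.5/0.2236 = 2.236; power Φ(2.236 − 1.96) = 61% (simulated 60%).
- Split, one visit: the information kept is φ(z)²/[p(1−p)] averaged over baseline, with p the response probability in Step 1 and z its normal quantile. This is about 0.55. Power is Φ(2.236√0.55 − 1.96) = 38% (simulated 39%).
- Continuous, five-visit average, all correlations equal: residual variance 6.25[(1+4r)/5 − r²] = 2.25; SE 1.5/√105 = 0.146; power Φ(3.416 − 1.96) = 93%.
- Split, five visits (logistic with patient-clustered errors), by simulation: 81%.

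Simulated power, continuous v split, n = 500, 10,000 runs per cell:

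| Outcome uses | Effect (points) | r = 0.4 | r = 0.8 |
|---|---|---|---|
| One visit | 0.5 | 60% v 39% | 92% v 76% |
| One visit | 0.7 | 88% v 64% | 99.7% v 96% |
| Five visits, equal correlation | 0.5 | 93% v 81% | 99% v 98% |
| Five visits, equal correlation | 0.7 | 99.7% v 98% | both about 100% |
| Five visits, neighbours more alike | 0.5 | 79% v 65% | 98% v 94% |
| Five visits, neighbours more alike | 0.7 | 97% v 91% | both about 100% |

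Type I error was 4.8% to 5.7% throughout. Capping VAS at 0 to 10 changes little. With 400 analysed (five visits, equal correlation, r = 0.4, 0.5 points) power is 86% v 72%. With SD 2.0 (one visit, r = 0.4, 0.5 points) it is 80% v 54%.

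**Step 3: does averaging over visits always help?** No. A 0.7-point effect at the first two visits only averages 0.7 × 2/5 = 0.28 over five; 0.28/0.146 = 1.913, so power is Φ(1.913 − 1.96) = 48% at r = 0.4. At one month alone the continuous model has 88% and the split about 65%. If the effect lasts three visits, the average has about 82%.

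**The case against.** **Baseline VAS is a legitimate predictor.** Aim 2 asks who succeeds, and baseline pain may validly predict who crosses the threshold. If VAS is entered as listed, the regression is already adjusted for it. This stands. A reader might infer that the plan's regression ignores baseline, or that the investigators intend to claim that worse pain benefits more; the documents support neither. What remains is an unadjusted group comparison and a coefficient with no guidance on how to read it.

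**The yes/no regression is inferred.** True. The responder comparison, however, is explicit, and the predictor model has no stated continuous outcome.

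**Not every predictor is affected.** A reader might infer that the split costs information on all of them. The ANOVA keeps OA grade on the score scale, and the Samilson and Prieto classification is the only severity grading that the documents define. The loss concerns the other Aim 2 factors.

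**The loss is modest on the likelier reading.** The term multi-level, with five surveys, suggests repeated visits. On that reading the loss is about 1 to 14 percentage points for a 0.5-point effect, and about 6 at most for 0.7 points with 500 analysed. This stands; the large gaps need a single visit and a small effect.

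**A five-visit average is a preference, not a correction.** This also stands: Step 3 shows that it can do worse than a one-month split when an effect fades early. The Background reports significant relief only at one month, although that study gave three injections.

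**Conclusion.** The point holds as a worthwhile, inexpensive improvement; it does not show that Aim 2 is invalid. The direction of the coupling needs only r below 1 with similar SDs at baseline and follow-up. Its size (odds ratio about 1.55 to 1.25 per point; a gap in baseline means of about 2.2 points at r = 0.4 and 1.3 at r = 0.8) rests on the assumed SD and correlations.

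The power loss rests on the further inference that the regression outcome is yes/no. It is clear if one visit defines response and the effect is small, and minor for larger effects, higher r or five visits. Absolute powers shift with the assumed SD, so the contrasts matter more than the levels.

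The unnamed visit, VAS item and model levels are a separate gap in specification. They matter here only because they leave open which row of the table applies.

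**What to change.** Alongside the responder analysis, add to the Data Analysis part of section 6 a multi-level linear regression of continuous follow-up VAS on the Aim 2 factors. It should use the five visits within patient and adjust for baseline VAS of the same item. Report visit-specific effects, from predictor-by-time terms, as well as the average.

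Whether the main contrast is the average or a named visit is for the investigators to decide, but it should be fixed before analysis. So should the VAS item. The Background does not single one out: "This improvement was significant for both pain at night, as well as pain with activity".

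Keep the analysis of response above 1.4 points for the same item, adjusted for baseline VAS. Adjust the responder v non-responder comparison in the same way, and show baseline VAS in both groups. State that the baseline VAS coefficient is not evidence of greater benefit. The continuous model does not remove this problem, so the statement is needed for both models.

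The cost is small. All the scores are already planned, as patients are surveyed "following the injection to complete the ASES, VAS pain (at rest, with activity, at night), and SST scores". Some results will be in VAS points rather than odds of success, which is why the responder analysis stays, and one VAS item must be chosen in advance.
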